
To be completed by study investigator(s) when they use the protocol

[Principal investigator institution name] Address	
name, degrees, job title	name, degrees, job title
name, degrees, job title	name, degrees, job title
name, degrees, job title	name, degrees, job title

[Sponsor name] Address	
name, degrees, job title	name, degrees, job title
name, degrees, job title	name, degrees, job title
name, degrees, job title	name, degrees, job title

Collaborating Institutions	Study Sites

4 Abstract

This section should be filled out with the following information.

Title:

Rationale and background:

Research question and objectives:

Study design:

Population:

Variables:

Data sources:

Study size:

Data analysis:

Milestones:

5 Amendments and Updates

<<to be filled upon actual protocol>>

6 Milestones and Timeline

This section should be filled out with the following information, when the study is implemented.

Milestone	Date
Start of data collection	
End of data collection	
<Study progress report(s) 1>	
<Study progress report(s) 2>	
<Study progress report(s) 3>	
<Interim report 1>	
<Interim report 2>	
<Interim report 3>	
<Registration in the EU PAS Register>	
Final report of study results	

EMA = European Medicines Agency; EU PAS Register = European Union Electronic Register of Post-Authorisation Studies.

7 Rationale and Background

The novel coronavirus SARS-CoV-2, the cause of COVID-19, has led to a global pandemic. Several COVID-19 vaccine candidates are currently under research and in development. COVID-19 vaccines may be licensed by the European Medicines Agency (EMA) following what is likely to be an accelerated investigational and licensing procedure. Because the pre-licensure period is short and number of participants in clinical studies is limited, monitoring of the safety of vaccines in the post-introduction phase will be needed in an efficient manner, with the objective of identifying, assessing and evaluating as rapidly as possible any unintended side effects of vaccination.

As per EC communication in October 2020¹, Member States and public health authorities should prepare to undertake studies of vaccine effectiveness and safety via coordination by the European Medicines Agency and the European Centre for Disease Prevention and Control, and specifically to prepare for participation in large-scale EU-wide effectiveness and safety monitoring studies.

As part of the preparedness activities for safety surveillance of COVID-19 vaccines, this template protocol provides a template for quickly developing a full study protocol to perform vaccine safety evaluation studies to quantify potential risks through the secondary use of electronic healthcare databases. The ACCESS project has developed several template protocols, that address: vaccine coverage, vaccine effectiveness and vaccine safety.

To allow all countries to participate and to utilize maximum capacity in Europe, protocols are divided in those that use primary data collection (e.g. hospital based), and those that rely on the secondary use of available electronic health care data.

This template safety protocol is for the evaluation of safety of COVID-19 vaccine(s) using population based electronic health record databases in Europe. In order to use this specific protocol, electronic health care data on population, events and COVID-19 vaccine administration are required.

The potential designs for safety evaluation of vaccines studies include the cohort, case-control, self-controlled case series (SCCS), self-controlled risk interval (SCRI), and case-crossover (CCO). Electronic health care data source requirements for the application of each study design are described in **Table 1**.

Table 1. Linkable electronic health care data elements for Cohort, Case-Control, SCCS, SCRI, and CCO designs

Design	Data Elements			
	Listing of all population members	Events	Covariates	Vaccine
Cohort	✓	✓	✓	✓
Case-Control	✓	✓	✓	✓
SCCS	X	✓	✓	✓

¹ https://ec.europa.eu/health/sites/health/files/vaccination/docs/2020_strategies_deployment_en.pdf

SCRI	X	✓	✓	✓
Case-Crossover	X	✓	✓	✓

Checkmark indicates design requires data element or feature; X indicates data element or feature is not required

As part of the harmonization of COVID-19 vaccine safety monitoring during the clinical development phase, the Coalition for Epidemic Preparedness Innovations (CEPI) has created a preliminary list of AESI for COVID-19 vaccine safety monitoring together with the Brighton Collaboration (SPEAC, 2020).

Within the ACCESS project, a list of AESI has been created which was approved by EMA (*EUPAS37273*). The listed AESI may not become real safety concerns but we should be ready to address them as they might potentially derail vaccination programs if they occur.

Although there will be readiness to address the AESI currently identified potential unexpected safety concerns related may arise during product development or after licensure; we aim that principles and designs in this protocol can also be applied to novel issues, which is why we created a decision framework to quickly assess which design may be most appropriate.

Each of the AESI listed in **Table 2** differs in terms of latency, acuity of onset, availability of empirical estimates for appropriate risk periods, and the effect of the event on subsequent likelihood of vaccination.

Criteria for determining the appropriate design for the event under study are described in **Annex 3**. Specific design recommendations for each AESI are provided in **Table 2** below.

Table 2. Assessment of the Suitability of Cohort, Case-Control, SCCS, SCRI and CCO designs for signal evaluation, by pre-identified AESI

Event	Cohort	Case-control	SCCS	SCRI	CCO
Enhanced disease following immunisation	X	✓	X	X	X
Multisystem inflammatory syndrome in children	✓	✓	✓ ^a	✓ ^a	✓
Acute respiratory distress syndrome	✓	✓	✓	✓	✓
Acute cardiovascular injury, including microangiopathy, heart failure, stress cardiomyopathy, coronary artery disease, arrhythmia, myocarditis	✓	✓	✓	✓	✓
Coagulation disorder, including deep vein thrombosis, pulmonary embolus, cerebrovascular stroke, limb ischaemia, haemorrhagic disease	✓	✓	✓	✓	✓
Generalised convulsion	✓	✓	✓	✓	✓
Guillain Barré Syndrome	✓	✓	✓	✓	✓
Diabetes (type 1 and unspecified type)	✓	✓	✓	X	X
Acute kidney injury	✓	✓	✓	✓	✓
Acute liver injury	✓	✓	✓	✓	✓
Anosmia, ageusia	✓	✓	✓	✓ ^a	✓
Chilblain-like lesions	✓	✓	✓	✓	✓
Single organ cutaneous vasculitis	✓	✓	✓	✓ ^a	✓

Event	Cohort	Case-control	SCCS	SCRI	CCO
Erythema multiforme	✓	✓	✓	✓ ^a	✓
Anaphylaxis	✓	✓	✓	✓	✓
Death (any causes)	✓	✓	✓	✗	✓
Sudden death	✓	✓	✓	✗	✓
Acute aseptic arthritis	✓	✓	✓	✓	✓
Meningoencephalitis	✓	✓	✓	✓	✓
Acute disseminated encephalomyelitis	✓	✓	✓	✓ ^a	✓
Narcolepsy	✓	✓	✓	✗	✗
Thrombocytopenia	✓	✓	✓	✓	✓
Transverse myelitis	✓	✓	✓	✓ ^a	✓
Preterm birth	✓	✓	✗	✗	✗
Major congenital anomalies	✓	✓	✗	✗	✗
Microcephaly	✓	✓	✗	✗	✗
Fetal growth restriction	✓	✓	✗	✗	✗
Gestational diabetes	✓	✓	✗	✗	✗
Preeclampsia	✓	✓	✗	✗	✗
Spontaneous abortions	✓	✓	✗	✗	✗
Stillbirth	✓	✓	✗	✗	✗
Induced abortions	✓	✓	✗	✗	✗
Termination of pregnancy for fetal anomaly (TOPFA)	✓	✓	✗	✗	✗
Neonatal death	✓	✓	✗	✗	✗
Maternal death	✓	✓	✗	✗	✗

^a Suitability of the self-controlled designs is dependent upon availability of a purported risk period, which for some AESI is as yet unknown.

8 Research Question and Objectives

Note to future investigators using this template to develop a full study protocol: the wording of some sections of this protocol can be retained as-is or modified as appropriate in a final study protocol. Notes directly to the investigators in these sections are indicated in square brackets. As there are multiple potential COVID-19 vaccine products under development and additional adverse events may be identified, this protocol template refers generically to a <<COVID-19 vaccine product>> and at times, <<event>> which may be replaced with the name of the specific vaccines or adverse events being investigated. The language in some sections, however, describes general principles, issues, and considerations for the investigator and will require the investigator to develop those sections with study-specific content, as appropriate for the specific study being considered.

[For all designs, the secondary analysis of vaccine groups defined by vaccine platforms or components should be done if the products are hypothesized to have a similar safety profile across the grouped products. Also, if a safety concern for an adverse event has arisen around a specific vaccine product, then the analysis of all COVID-19 vaccine products combined should not be conducted for that event]

Primary objective: To determine whether there is an increased risk of pre-specified <<event>> following vaccination with specific <<COVID-19 vaccine product>> using study designs <<cohort, case-control, self-controlled, or case-crossover>> which allow for control of confounding.

Secondary objectives:

§ To determine whether there is an increased risk of pre-specified <<event>> in specific vaccine groups defined by platform and/or components (e.g. adjuvant)

§ To determine whether risk of <<event>> following vaccination with specific <<COVID-19 vaccine product>> differs by characteristics such as age, sex, comorbidities, infections, concomitant vaccinations, concomitant medications, and/or other characteristics.

9 Research Methods

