9.2.3 Variables

9.2.3.1 Event Assessment

In this section, the operational definitions for identifying each <<event>> should be described, with reference to code lists included in a separate protocol appendix.

Definitions, codes, and proposed algorithms for all AESI can be found at https://drive.google.com/drive/folders/1Y_3cuGRN1g-jBv2ec1fC0aYcpxEjtrY9. These AESI definition templates can serve as example for event definitions forms for non-anticipated events.

Note: The AESI event definitions forms documents will be evolving based on experience in the calculation of background rates in the ACCESS project (EUPAS37273).

<<Event>> should be identified in each participating database using diagnosis codes, where possible algorithms should be used to ascertain the event or for sensitivity analyses. Performance of algorithms should be benchmarked by comparing incidence rates with published rates and between databases as described in ADVANCE (Sturkenboom, 2020). The provenance of diagnosis codes (e.g. hospital vs. general practice) should be considered in development and application of event algorithms (Gini, 2019).

For signal evaluation studies event identification algorithms should be validated using chart abstraction or manual verification of electronic records while being blinded to the <<COVID-19 vaccine>> exposure. If resources are restricted a sample may be validated initially to assess the positive predictive value (PPV). If the PPV is below 80% all cases should be validated.

Certainty of the diagnosis of an event should be classified against the existing and new Brighton Collaboration (BC) case definitions. SPEAC is providing a toolbox to those case definitions which is accessible from the Brighton Collaboration website or by writing to the [contact]. Analysis may be restricted to specific BC level cases for case-based analyses, whereas sensitivity analyses and cohort incidence estimations may focus on inclusion of lowest level of diagnostic certainty.

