9.2.3.3 Risk & Control periods

In this section, risk and control windows should be specified for each of the events under assessment for the specific design.

The duration of the risk periods should be specific for each of the outcomes and defined to establish an accurate relationship and patterns in that relationship. Risk windows should be subdivided in smaller periods of risk to allow for investigation of changes in the estimate of risk and doses. Control periods should be chosen in a manner that there is no misclassification of exposure/event occurrence.

As general reference for risk periods and opportunity to harmonize we recommend inspection of outputs of the SPEAC project as this is creating event definition, codes, risk factors and windows for many of the AESI which will be released on the Brighton Collaboration website in the coming year (<https://brightoncollaboration.us>).

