9.6 Data Analysis

9.6.1 Descriptive Analysis

Attrition diagrams demonstrating the loss of subjects applying inclusion and exclusion criteria should be provided.

For each study design, demographic characteristics of the study population (e.g. age at study entry, sex) and baseline characteristics (eg. co-morbidities) should be summarized for each data source using descriptive statistics. Description of <<COVID-19 vaccine>> type should be described and along with counts of exposure by calendar month to allow for inspection of time trends.

The distributions of the characteristics by study groups (index/comparison cohorts or cases/controls) should be presented in tables to demonstrate potential differences/or lack thereof between groups. For propensity matched cohorts the distribution and propensity scores should be plotted prior to the matching and balance after matching should be shown.

Counts and percentages should be presented for categorical variables (age at study entry in categories, sex, race/ethnicity, comorbidities). Mean, standard error, median and range should be presented for continuous variables (age at study entry). The missingness of variables should also be described.

Event counts should be provided categorized by level of severity/certainty. Appendices should provide code /algorithm counts for the events.

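### Table 2 ticks all five designs for two mixed event rows, in conflict with Annex 3 on stroke and myocardial infarction; adopting such a row as the event can also dilute a risk in a rare component

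*Protocol*

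**What the plan says.** Table 2 in section 7 is titled "Assessment of the Suitability of Cohort, Case-Control, SCCS, SCRI and CCO designs for signal evaluation, by pre-identified AESI", and the text above it presents it as the source of design recommendations for each AESI. Two rows under its Event column are groups:

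- The cardiovascular row reads "Acute cardiovascular injury, including microangiopathy, heart failure, stress cardiomyopathy, coronary artery disease, arrhythmia, myocarditis".
- The row that joins clotting and bleeding conditions reads "Coagulation disorder, including deep vein thrombosis, pulmonary embolus, cerebrovascular stroke, limb ischaemia, haemorrhagic disease".

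Both rows tick cohort, case-control, SCCS, SCRI and CCO. Neither carries footnote a, the table's only qualification, which concerns unknown risk periods.

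Annex 3 gives the criteria on which these ratings should rest. It has one line for recurrent events that are not independent, with stroke as its example. Another line covers events that censor observation, including outcomes that make death more likely, with myocardial infarction as its example.

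Elsewhere the template leaves the event open. Section 8 says the event placeholder is one "which may be replaced with the name of the specific vaccines or adverse events being investigated". Section 9.2.3.1 says that "the operational definitions for identifying each <<event>> should be described, with reference to code lists included in a separate protocol appendix". Section 9.2.3.3 says: "The duration of the risk periods should be specific for each of the outcomes". Section 9.6.1 says: "Appendices should provide code /algorithm counts for the events".

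**The concern.** The template is meant for building full protocols quickly, so users are likely to take the Table 2 ratings as they stand. One rating for a row of unlike conditions can be right for some components and wrong for others, and the grouping hides this. A user evaluating stroke would read an unqualified tick for SCRI, which Annex 3 calls unsuitable for exactly that example.

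A second consequence follows if the row itself is entered as the event. A composite rate ratio averages the component ratios, weighted by their background frequency. A large relative risk in an uncommon component then contributes little to the estimate, while the primary objective is to determine whether risk is increased. Section 8 tells users not to pool all vaccine products when a concern is specific to one product, but gives no matching caution about pooling events. The subgroup analyses (9.6.4) concern effect modifiers, and the listed sensitivity analyses (9.6.5) do not break an event into its components.

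**Working it through.** **1. Table 2 against Annex 3.** This part needs no assumed figure.

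| Source | Cohort | Case-control | SCCS | SCRI | CCO |
|---|---|---|---|---|---|
| Table 2, coagulation row (names stroke) | ✓ | ✓ | ✓ | ✓ | ✓ |
| Annex 3, dependent recurrent events (example: stroke) | ✓ | ✓ | O, with adaptation | X | O |
| Table 2, cardiovascular row (names coronary artery disease) | ✓ | ✓ | ✓ | ✓ | ✓ |
| Annex 3, event censors observation (example: myocardial infarction) | ✓ | ✓ | X | X | ✓ |

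For stroke the conflict is direct: the same condition is named in both places, and three of the five ratings differ. For the cardiovascular row it takes one step of inference, because Table 2 names coronary artery disease and Annex 3 names myocardial infarction, an acute form of it. Two of the five ratings then differ.

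**2. Dilution if a row is used as the event.** The protocol states no event count, effect size, power or component share (section 9.4 leaves study size to the investigator), so there is no figure of its own to reproduce. The following is illustrative.

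Assumptions: the component has a share f of background composite events and rate ratio RR; all other components have rate ratio 1. Then

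composite RR = 1 + f × (RR − 1).

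| f | RR = 3 | RR = 5 | RR = 10 |
|---|---|---|---|
| 1% | 1.02 | 1.04 | 1.09 |
| 2% | 1.04 | 1.08 | 1.18 |
| 5% | 1.10 | 1.20 | 1.45 |
| 10% | 1.20 | 1.40 | 1.90 |
| 50% | 2.00 | 3.00 | 5.50 |

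**3. Whether the diluted effect is missed.** Take risk and control windows of equal length, as in the 42/42-day example under Figure 4, with E background composite events per window. Use a normal test of log RR, two-sided 5%:

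SE = √(1/E + 1/(E × RR)); power = Φ(ln RR / SE − 1.96).

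Worked case with E = 200, f = 2%, RR = 5:

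- Composite: RR = 1.08, SE = √(1/200 + 1/216) = 0.098, ln 1.08 / 0.098 = 0.78, power 12%.
- Component alone: E = 4, SE = √(1/4 + 1/20) = 0.548, ln 5 / 0.548 = 2.94, power 84%.

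Power at RR = 5 for other shares and event counts:

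| E per window | f | Composite | Component alone |
|---|---|---|---|
| 200 | 1% | 6% | 55% |
| 200 | 2% | 12% | 84% |
| 200 | 5% | 48% | >99% |
| 2,000 | 1% | 24% | >99% |
| 2,000 | 2% | 70% | >99% |
| 2,000 | 5% | >99% | >99% |
| 10,000 | 1% | 80% | >99% |
| 10,000 | 2% | >99% | >99% |

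The normal approximation is rough for the smallest component counts. An exact conditional test at E = 200 gives a similar picture: 5%, 11% and 46% for the composite against 56%, 90% and >99% for the component.

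**The case against.** The strongest reply is that Table 2 defines no endpoint. Its title says it rates designs; section 8 lets the user name the specific event; section 9.2.3.1 leaves the definition and code list to the study protocol; section 9.2.3.3 already asks for outcome-specific risk periods. A study prompted by a myocarditis signal can enter myocarditis without departing from the template. The word "including" in both rows fits a heading over several conditions at least as well as a prescribed composite. The event definition forms are in an external folder that is not at hand, and they may treat the components separately. The network design also allows for large event counts.

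All of that stands against a stronger reading that a reader might infer: that the plan makes these rows single endpoints, each with one risk window, one validation result and one estimate, and that a real effect is therefore missed. No section says so, and whether the effect is missed turns on shares and counts the protocol does not give.

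Three further extensions also lack support. The row "Diabetes (type 1 and unspecified type)" might be cited as a third case, but no share for type 1 is given and the wording may only reflect codes that do not record type. Opposite effects on clotting and bleeding might be said to cancel, but that is hypothetical, and Annex 3 draws no such distinction. Nor does Annex 3 classify heart failure as gradual or myocarditis as acute.

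The reply does not answer the design ratings. Giving them is Table 2's stated purpose, and for stroke they contradict Annex 3 whatever event the user later defines. It also leaves in place that nothing in sections 9.6.1, 9.6.4 or 9.6.5 asks for component-level estimates; the code counts in 9.6.1 are descriptive.

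**Conclusion.** The point holds in two parts of unequal strength.

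The firm part is an internal contradiction. Table 2 and Annex 3 disagree on SCCS, SCRI and CCO for stroke, and on SCCS and SCRI for the coronary component if myocardial infarction is taken to fall within it. It rests on no assumed number.

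The conditional part is dilution. It arises only if a user adopts a whole row as the event. With an assumed RR of 5 and a 1-2% share, the composite ratio is 1.04-1.08. Composite power is then 6-12% at 200 background events per window, 24-70% at 2,000, and 80% or more at 10,000. At shares of 5-10% the same RR gives 1.20-1.40, which is easier to see. Dilution is a risk the template leaves open, not a result it produces, and alone it would justify clarification and no more.

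**What to change.** In Table 2, either split the cardiovascular and coagulation rows into their named components, or state that the two rows are headings and not events for analysis. In both cases, say that each component is to have its own Annex 3 design rating, risk period, validation and effect estimate, with any composite reported as a secondary summary. Reconcile the stroke and coronary ratings in Table 2 with the corresponding Annex 3 lines, and carry over Annex 3's conditions as footnotes where a rating is conditional.

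The cost is template wording and more output tables from the same data. The statistical price is fewer events in each analysis, so wider intervals for the rarest components, and more estimates to interpret side by side.

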Annex 2. ENCePP Checklist for Study Protocols

The ENCePP Checklist for Study Protocols can be accessed and downloaded using the following link:
[http://www.encepp.eu/standards and guidances/checkListProtocols.shtml](http://www.encepp.eu/standards_and_guidances/checkListProtocols.shtml)

Annex 3. Criteria to determine whether Cohort, Case-Control, Self-Controlled Case Series, Self-Controlled Risk Interval or Case-crossover Can Be Used for Signal Evaluation

Based on the assumptions and requirements of each design, we provide a decision framework for determining when Cohort, Case-Control, Self-Controlled Case Series (SCCS), Self-Controlled Risk Interval (SCRI), and Case-Crossover (CCO) designs can be used for signal evaluation.

The decision framework described below is based on event criteria. However, the identification of a suitable comparator group (active or unvaccinated) and the ability to identify major confounders should also be considered to determine the appropriate study design (see [section 9.1](#)). Cohort and case-control designs are suitable to assess a majority of events. In general, when the data is already available in electronic health care databases, cohort analysis should be conducted since it will provide absolute and relative risk measures. Case control design may be efficient if additional data needs to be collected or exposure patterns are difficult to track over follow-up time, also they allow for matching on calendar time, which is relevant with strong temporal trends. Because cohort and case control designs use other subjects as comparator, residual confounding due to factors that are not easily measurable in EHR data (such as genetics, habits, socio-economic status, ethnicity) can remain. If this is suspected self-controlled designs may be more suitable, but they require accurate estimation of the risk window and onset of the event.

Decision Framework for Determining Suitability of cohort, case-control, SCCS, SCRI, CCO for signal evaluation

Event criteria	Cohort	Case-control	SCCS	SCRI	CCO
Event latency					
Long latency	✓	✓	○ ^a	✗	✗
Short latency	✓	✓	✓	✓	✓
Outcome onset					
Acute onset	✓	✓	✓	✓	✓
Gradual onset	✓	✓	○ ^a	✗	✗
Ability to define risk period for outcome following exposure					
Can be clearly defined	✓	✓	✓	✓	✓
Cannot be clearly defined	✓	✓	○	✗	✗
Effect of event on likelihood of vaccination					
Event does not affect likelihood of vaccination	✓	✓	✓	✓	✓

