Event temporarily decreases or increases likelihood of vaccination	✓	✓	✓	✓	✓
Event is a (permanent) contraindication to vaccination	O ^b	O ^b	O ^b	O ^b	✓
Event censors the period of observation for exposure (e.g., death or an outcome that increases the probability of death such as myocardial infarction)	✓	✓	X	X	✓
Event is independently recurrent	✓	✓	✓	✓	✓
Event is non-recurrent but rare	✓	✓	✓	✓	✓
Event is recurrent, and recurrent events are not independent (e.g., stroke)	✓	✓	O ^c	X	O
Temporal trends in vaccination					
Temporal trends in vaccination are not present during the study period	✓	✓	✓	✓	✓
Temporal trends in vaccination are present during the study period	✓	✓	✓	✓	O

Checkmark indicates design is suitable; X indicates not suitable; O indicates that the study design is possible under certain circumstances.

^a Suitable if prodromal symptoms before diagnosis of the outcome do not cause or prevent vaccination, either temporarily or permanently. To address this potential source of bias, every effort should be made to identify the onset of symptoms from the available data such as medical records, rather than relying on the date of diagnosis.

^b Suitable if the vaccine is given in a single dose. If the vaccine is given in multiple doses, the design is not suitable unless special analytic techniques are applied to handle censored, perturbed, or curtailed post-event exposures.

^c Suitable if appropriate adaptations to the self-controlled case series are applied (Farrington, 2010)

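### Table 2 recommends self-controlled designs that the Annex 3 criteria mark unsuitable: SCCS for death, SCRI for stroke and, by category, both for infarction-type events

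*Protocol*

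**What the plan says.** Section 7 links the two tables. It states: "Criteria for determining the appropriate design for the event under study are described in" Annex 3, and then: "Specific design recommendations for each AESI are provided in" Table 2. Table 2 is therefore offered as the result of applying Annex 3 to each event.

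Table 2 ticks SCCS for the row beginning "Death (any causes" and for sudden death, with no footnote; it crosses SCRI in both rows. It ticks all five designs, again with no footnote, for "Acute cardiovascular injury, including microangiopathy, heart failure, stress cardiomyopathy, coronary artery disease, arrhythmia, myocarditis" and for coagulation disorder, a row that includes cerebrovascular stroke. The only footnote to Table 2 concerns risk periods that are not yet known, and it is not attached to any of these four rows.

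Annex 3 has two rows that bear on these events. The first begins "Event censors the period of observation for exposure (e.g., death or an outcome that increases the probability of death such as myocardial infarction" and marks SCCS and SCRI X, with cohort, case-control and CCO ticked. The second begins "Event is recurrent, and recurrent events are not independent (e.g., stroke" and marks SCCS O (footnote c: suitable with adaptations), SCRI X and CCO O. Under the Annex 3 key, X means not suitable and O means possible in certain circumstances.

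**The concern.** Table 2 is the look-up an investigator would use when a signal has to be evaluated quickly, and Section 9.1 tells the user to pick one design and delete the text for the others. A wrong tick would therefore be copied into a study protocol.

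Death is the serious case. Section 9.1.3.1 restricts SCCS to people who were vaccinated and had the event, and takes as control time everything in the observation period outside the risk window. A person who dies before vaccination cannot enter such a dataset, so any pre-vaccination control time is free of deaths by construction. If observation is cut at death, its length depends on the event itself. Either feature can move the rate ratio away from 1 when the vaccine has no effect. Nothing elsewhere repairs this: Table 4 names only conditional Poisson regression for self-controlled designs, and the limitations in Section 9.8 do not mention event-dependent observation for them.

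**Working it through.** **1. The cells side by side.**

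| Event | Design | Table 2 | Annex 3 | Result |
|---|---|---|---|---|
| Death, sudden death | SCCS | tick | X (death named) | direct contradiction |
| Death, sudden death | SCRI | X | X | agree |
| Death, sudden death | CCO | tick | tick | agree |
| Stroke (within coagulation disorder) | SCRI | tick | X (stroke named) | direct contradiction |
| Stroke | SCCS | tick | O, footnote c | condition omitted |
| Stroke | CCO | tick | O | condition omitted |
| Infarction-type (within cardiovascular injury) | SCCS, SCRI | tick, tick | X, X (myocardial infarction named) | contradiction by category |

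The last row is an inference: Table 2 names coronary artery disease, not myocardial infarction.

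**2. Size of the problem for death.** The protocol gives no rates, roll-out or sample size, so all inputs here are assumptions: no vaccine effect (true ratio 1.00), one dose, deaths uniform over T days, planned vaccination uniform over the first M days, risk window of R days, and only people vaccinated before death kept. With e exposed days, u unexposed days and y = 1 if the event falls in the risk window, the SCCS estimate exp(b) solves

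Σ [ y − exp(b)·e / (exp(b)·e + u) ] = 0.

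For a short window this is close to the observed share of events in the window divided by the mean of e/(e + u), which can be worked by hand.

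- T = M. Given v < d, the observed share is 2R/T. With observation to the planned end, the expected share is R/T, so the ratio is 2.0. Cut at death, the expected share is the mean of R/d where d has density 2d/T², which is 2R/T, so the ratio is 1.0.
- T = 365, M = 180. The area with v < d is 365×180 − 180²/2 = 49,500, so the observed share is 180R/49,500 = R/275. To the planned end the ratio is 365/275 = 1.33. Cut at death, the expected share is R·180·(1 + ln(365/180))/49,500, so the ratio is 1/(1 + 0.707) = 0.59.

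A simulation of 400,000 histories per scenario gives the same values at R = 2, apart from the finite window and sampling error, and extends them to longer windows:

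| T, M | R | cut at death | planned end |
|---|---|---|---|
| 365, 365 | 2 / 28 / 42 | 1.04 / 1.18 / 1.29 | 2.01 / 2.10 / 2.14 |
| 365, 180 | 2 / 28 / 42 | 0.59 / 0.63 / 0.67 | 1.33 / 1.37 / 1.39 |
| 180, 180 | 2 / 28 / 42 | 1.04 / 1.37 / 1.69 | 2.00 / 2.21 / 2.36 |

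**3. Infarction- or stroke-type events.** Assumed: case fatality 10% to 50%, mean 7 days from event to death.

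- SCCS (R = 42, T = 365, M = 180): 0.95 down to 0.81 if cut at death; 1.03 up to 1.15 with the planned end.
- SCRI with the 42/42-day windows of the Figure 4 example, single dose: 0.88 down to 0.43 if follow-up is curtailed at death; 1.00 if the fixed windows are kept.

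**The case against.** The other side has several good points.

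- A reader might infer that Annex 3 rules out SCCS for stroke. It does not: the row naming stroke makes SCCS conditional on adaptations. SCCS would become X only if stroke were also read into the censoring row, which does not name it. The defect in that cell is a missing condition.
- A reader might infer that every Table 2 tick facing an Annex 3 O is a contradiction. Table 2 has no O symbol, and a tick is the nearest mark to a design that is possible under conditions. The plain SCCS ticks for diabetes and narcolepsy are therefore a matter of notation. Footnote a refers to self-controlled designs generally, so its wording already reaches SCCS. What remains is the plain CCO tick for events flagged as having an unknown risk period, where the Annex 3 row "Cannot be clearly defined" gives CCO X. Even there, not yet known is not the same as not definable.
- A reader might infer that the row "Enhanced disease following immunisation" is wrong because Annex 3 treats cohort and case-control alike in every row. Annex 3 says that comparator availability and identification of confounders also count, so different marks are not shown to be an error.
- A reader might infer that following Table 2 always gives a biased answer. Table 3 ends SCCS follow-up at censoring conditions, so the planned-end figures are not its plain reading, and with cutting at death some scenarios are near null (1.04). Table 3 also starts follow-up when the last inclusion criterion is met. If that means the dose, there is no pre-vaccination time, and with a planned end the single-dose bias disappears; cutting at death would still bias the estimate.
- The document is a template. It requires a feasibility assessment, and Annex 3 favours a cohort analysis when the data are already in electronic databases, so Table 2 alone does not settle the design.

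These points narrow the finding. They do not remove the direct contradictions, and the protocol does not say which table prevails.

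**Conclusion.** The point holds in a limited form. Table 2 contradicts its own stated criteria explicitly in three cells: SCCS for death, SCCS for sudden death, and SCRI for the row containing stroke. It does so by category for SCCS and SCRI with infarction-type events, and it drops the Annex 3 conditions on SCCS and CCO for stroke. This rests on the text alone.

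The consequence is a risk of bias, not a certainty. For a standard SCCS on death the null rate ratio can fall well below or well above 1, so a false signal and a masked one are both possible. The size and direction depend on the assumed roll-out, the risk window and whether observation is cut at death. For infarction and stroke the bias grows with case fatality and may be absent for a single-dose SCRI with fixed windows.

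**What to change.** In Table 2:

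- Death and sudden death: change SCCS to X.
- Coagulation disorder: for stroke, set SCRI to X, SCCS to O with Annex 3 footnote c, and CCO to O.
- Acute cardiovascular injury: set SCCS and SCRI to X for infarction-type events that raise the probability of death.
- Split the two composite rows if their components need different marks, and add O to the Table 2 key.
- State that Annex 3 governs where the tables differ.

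If the authors want to allow an SCCS extension for event-dependent observation in the death rows, the Annex 3 cell and Table 2 should be amended together, since the Annex 3 X currently carries no exception.

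Two minor consistency edits: show the O condition for SCCS in the diabetes and narcolepsy rows, and reconcile the CCO ticks with Annex 3 for events flagged as having an unknown risk period. The enhanced-disease row needs no change on this ground.

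The cost is an edit to one table plus one sentence. Fewer simple self-controlled options remain for these events, but Table 2 already ticks cohort and case-control for all four of the main rows.
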